11.5 Calculation or derivation of pharmacodynamic variable(s) (Not applicable)

11.6 Calculation or derivation of pharmacogenetic variables (Not applicable)

11.7 Calculation or derivation of health economic variables (Not applicable)

12. STATISTICAL METHODS AND SAMPLE SIZE DETERMINATION

Statistical analyses will be performed by _____ using SAS[®] version 9.2 or higher and, where appropriate, additional validated software.

12.1 Description of analysis sets

12.1.1 Safety analysis set

All healthy volunteers who received at least 1 dose of [¹⁴C]-selumetinib IP and for whom any postdose data are available will be included in the safety population.

12.1.2 Pharmacokinetic analysis set

The PK analysis set will include all healthy volunteers who receive at least 1 dose of [¹⁴C]-selumetinib and have at least 1 postdose PK measurement without important protocol deviations/violations or events thought to significantly affect the PK of the IP.

12.2 Methods of statistical analyses

Statistical analysis will be performed by _____ Global Phase 1 Services using Standard Operating Procedures and Work Instructions, unless otherwise specified. Statistical analysis will be carried out by using the SAS[®] software. Other analyses than those stated below might be performed to gain information needed for the planning and analyses of future studies.

12.2.1 General principles

Given the exploratory nature, no formal statistical hypothesis testing will be performed in this study.

The statistical analysis will be descriptive and consist of subject listings, graphs, and summary statistics comprising geometric mean, coefficient of variation (CV%), arithmetic mean, standard deviation (SD), median, minimum (min), and maximum (max) values as appropriate.

Missing data will be assumed to be missing completely at random, causing a reduced sample size. Since the descriptive statistics will be presented in tables and individual data listings, no action will be taken to handle missing data.

A healthy volunteer who withdraws prior to the last planned observation in the study period will be included in the analyses up to the time of discontinuation.

Data from nonvalid healthy volunteers (healthy volunteers excluded from the analysis set[s]), which are recorded in the database, will only be presented in listings.

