3.1 Overall study design and flow chart

This is a phase 1, open label, single dose study to determine the rates and routes of elimination of a single dose of [¹⁴C]-selumetinib and its metabolites by assessment of concentrations of total [¹⁴C] radioactivity in blood and plasma, concentrations of selumetinib and N-desmethyl selumetinib in plasma and percent recovery of the radioactive dose in urine and faeces.

Approximately 6 healthy male volunteers, aged 50 to 65 years (inclusive), will be recruited at 1 study centre.

Healthy volunteers will be screened over a period of maximum 28 days for eligibility. Screening assessments include evaluation of clinical chemistry, haematology, urinalysis, a physical examination, vital signs, an echocardiogram, a full ophthalmological examination and paper ECGs. Study-related procedures will only be performed after signing of the informed consent form (ICF).

Eligible healthy volunteers will be admitted to the study centre visit on Day -1 predose.

Healthy male volunteers will receive a single dose of [¹⁴C]-selumetinib Hyd-Sulfate administered as 3 x 25 mg oral capsules on Day 1. Healthy volunteers will remain at the study centre up to 7 days following receipt of the IP when samples of blood, urine, and faeces will be collected. The length of the residential period may be reduced or extended if deemed appropriate based on emerging data. Once the mass balance cumulative recovery >90% has been achieved or <1% of the dose administered has been collected in urine and faeces within 2 consecutive days, healthy volunteers will be permitted to leave the study centre.

If emerging data indicates that adequate dose recovery has not been achieved after 7 days then these healthy volunteers may be asked to continue urine and/or faecal collections for a further 3 days either on an inpatient or an outpatient basis. If adequate dose recovery is still not achieved, these healthy volunteers could be asked to return to the study centre approximately 7 days later, for a further 24 hour collection. For these healthy volunteers, a final follow-up visit will take place on the last day of urine and/or faecal collection.

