The ratio of plasma selumetinib to plasma [^{14}C] radioactivity concentrations (expressed as a percentage) as well as the ratio of plasma N-desmethyl selumetinib to plasma [^{14}C] radioactivity concentrations (expressed as a percentage) for each sampling time will be listed by healthy volunteer and summarised using descriptive statistics, to assess the contribution of unchanged drug to the total radioactivity in plasma over time.

A subject listing of whole blood/plasma [^{14}C] radioactivity concentration-time ratios (expressed as a percentage) and percent distribution of radioactivity in blood cells will be presented and the data will be summarised by scheduled time using descriptive statistics.

Blood-based PK parameters will be summarised using descriptive statistics. Individual PK parameters will be presented along with descriptive statistics for all healthy volunteers.

Urine [^{14}C] radioactivity data will be summarised by scheduled collection intervals using descriptive statistics. Individual urine recovery data will be presented along with the descriptive statistics for all healthy volunteers.

Faecal [^{14}C] radioactivity data will be summarised using descriptive statistics. Individual faecal recovery data will be presented along with the descriptive statistics for all healthy volunteers.

The total recovery of radioactivity over the study duration will be computed as the sum of the cumulative excretion (as % of dose) in urine, faeces, and emesis (if any). Cumulative mean recovery of radioactivity-time profiles will be graphically presented for urine, faeces, and total (sum of urine plus faeces, plus emesis, if applicable). Individual cumulative recovery data (urine, faeces, and total) will be presented graphically and in tables along with the descriptive statistics for all healthy volunteers.

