12.2.2.1 Interim analysis

The bioanalytical laboratory will calculate percent of radioactive dose recovered in urine and faeces in support of healthy volunteer release criteria. These values will be used for interim reporting purposes only to track radioactive dose recovered on an ongoing basis. These results will be part of the radioactivity report which will be included as an appendix to the CSR. Following database lock, the percent of radioactive dose recovered in urine, faeces, and overall, and related parameters will be calculated following Standard Operating Procedures (SOPs) and rounding procedures as described above and in Section 11.4. The values calculated by will be considered the final study results and presented in the body of the CSR.

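### The missing-completely-at-random, no-action rule contradicts recovery-based release, so interval means and cumulative mean recovery curves average a changing, outcome-selected subset

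*Protocol*

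**What the plan says.** Section 12.2.1 gives one rule for all missing data, with no exception for urine or faeces: "Missing data will be assumed to be missing completely at random, causing a reduced sample size". Because results are descriptive and listed individually, "no action will be taken to handle missing data". A volunteer who withdraws "will be included in the analyses up to the time of discontinuation".

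Section 3.1, like the synopsis, makes the length of excreta collection depend on the recovery measured so far. Volunteers may leave on this condition: "Once the mass balance cumulative recovery >90% has been achieved or <1% of the dose administered has been collected in urine and faeces", the second part being judged within two consecutive days. It adds: "The length of the residential period may be reduced or extended if deemed appropriate based on emerging data". For the period after Day 7: "If emerging data indicates that adequate dose recovery has not been achieved after 7 days then these healthy volunteers may be asked to continue", for three more days and possibly one later 24-hour collection. Footnote d of Table 3 carries the same kind of rule. Section 12.2.2.1 confirms that the laboratory computes, on an ongoing basis, the "percent of radioactive dose recovered in urine and faeces in support of healthy volunteer release criteria".

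On reporting, Section 12.2.2 summarises urine radioactivity by scheduled collection interval, and "Cumulative mean recovery of radioactivity-time profiles will be graphically presented for urine, faeces, and total". Sections 11.4 and 12.2.2 define each volunteer's total recovery as the sum of his own cumulative excretion (with emesis, if any). No section says how a released volunteer enters time points after his release.

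**The concern.** Data are missing completely at random when their absence has nothing to do with the values. Here the absence of a late interval is decided by the quantity being measured. A volunteer with high recovery, or one whose excretion has nearly stopped, may leave; one with inadequate recovery may be asked to go on. The stated assumption is therefore false by design for the excreta data.

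This matters because the primary objective (Section 2.1) is the rates and routes of excretion. The rate part is read from the interval summaries and the cumulative mean curves. If a released volunteer simply drops out of the denominator, a later mean describes a different group from an earlier one. A mean cumulative recovery can then fall, which no individual's cumulative recovery can do, and a shift caused by who is left can be read as a feature of excretion.

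**Working it through.** The protocol's only design figure is the sample size of 6 (Section 12.3). It rests on previous similar studies and has no inputs to reproduce. The check is therefore to apply the release rules and compare two means at the same time point: the available-case mean (only those still collecting) and the mean over all six with released volunteers held at their last cumulative value. The recovery values below are assumptions; the documents give none.

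**1. High-recovery release.** Four volunteers stand at 92% and two at 80% at 168 h. The four leave and the two reach 84% by 240 h.
- At 168 h, n = 6: (4 × 92 + 2 × 80)/6 = 528/6 = 88.0%.
- At 240 h, available-case, n = 2: 84.0%.
- At 240 h, all six: (4 × 92 + 2 × 84)/6 = 536/6 = 89.3%.

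The plotted curve falls by 4.0 points although nobody's recovery fell. The interval summary errs the other way. The two remaining men add a mean of 4.0 points, so summing interval means gives 88.0 + 4.0 = 92.0%, against a mean total of 89.3%.

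**2. Low-excretion release.** Two volunteers have levelled off at 80% and leave under the 1% route, while four go from 84% to 92%.
- Before, n = 6: (2 × 80 + 4 × 84)/6 = 496/6 = 82.7%.
- After, available-case, n = 4: 92.0%.
- After, all six: (2 × 80 + 4 × 92)/6 = 528/6 = 88.0%.

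Here the available-case mean is 4.0 points too high, so the direction of the distortion is not fixed.

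**3. Release during the first week.** Cumulative recovery is taken as F × (1 − exp(−k × day)), with F = 95, 95, 94, 94, 93, 93% and k = 1.8, 1.5, 1.2, 0.8, 0.5, 0.4 per day. Each man leaves as soon as a rule permits.
- Release falls on days 2, 2, 3, 4, 7 and 9, so n over days 1 to 7 is 6, 6, 4, 3, 2, 2, 2.
- Day 5 cumulative mean: 82.9% available-case (n = 2), 88.3% with released men held at their last value (n = 6).
- Day 5 interval mean: 5.6% of dose available-case, 2.3% for all six on the assumed curves.
- Available-case interval means over seven days add to 105.3% of dose; the mean of per-volunteer totals is 90.8%.

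In this example the cumulative mean never falls. It is only too low.

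**4. Simulation.** 4,000 trials of six volunteers in each of 18 scenarios: mean plateau 90, 93 or 96% (SD 3), median rate 0.6, 0.9 or 1.3 per day, log-scale SD of the rate 0.3 or 0.5, seven days, and release taken as soon as permitted.
- The available-case cumulative mean fell at least once in 17% to 81% of trials.
- The 90th percentile of the largest one-day fall was 0.5 to 4.6 points.
- Interval means added to 0.9 to 10.4 points of dose more, on average, than the mean per-volunteer total.

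Any fall above 0.01 point was counted, and the median largest fall was between 0.0 and 0.7 points, so many of the falls are trivial.

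**The case against.** The strongest reply is that the shrinking denominator is inferred. The protocol never says that a released volunteer's cumulative recovery becomes missing. A cumulative percentage stays defined after the last collection, collections after permitted release can be read as not required, the sentence on discontinuation is worded for men who withdraw, and Section 12.2.2 presents cumulative recovery with statistics for all volunteers. An analysis plan, not shown here, could settle the matter. Individual recoveries are also tabulated and plotted and n is among the summary statistics, so with six men and no hypothesis test a change of composition would be visible.

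Much of this stands as a limit on the size of the harm. It does not remove the contradiction. The protocol is not silent: it fixes an unqualified assumption and a no-action rule, and an analysis plan that carried values forward would depart from that text. Individual plots let a reader detect the artefact but do not correct the summary.

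Two stronger readings are tempting. A reader might infer that final overall recovery is understated. It is not: the total is formed per volunteer up to his own last collection, so a released man keeps his value, and in the first example the mean total is 89.3%, the correct all-six figure. A reader might also infer that late means come from slow excretors only. That fits the 90% route and the collections after Day 7, but not the 1% route, by which a man with low recovery may leave.

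Early withdrawal is a separate matter from release. Withdrawn volunteers are not replaced (Section 5.9), and one with a single postdose measurement can stay in the PK set (Section 12.1.2). With five men at 92% and one withdrawn at an assumed 30%, the mean is (5 × 92 + 30)/6 = 81.7%. The documents do not support excluding such a man as the one correct analysis, because that needs its own assumption that withdrawal is unrelated to recovery.

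**Conclusion.** The point holds in a limited form. For excreta, the missing-data rule in Section 12.2.1 is contradicted by the release and extension rules in Section 3.1, the synopsis and Table 3. Applied literally, it makes the interval means and the cumulative mean recovery profiles available-case means over an outcome-selected subset. Overall urinary, faecal and total recovery per volunteer are not distorted by release.

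The size cannot be fixed from the documents. In the hand examples the cumulative mean was off by 4.0 to 5.4 points in either direction (84.0 against 89.3, 92.0 against 88.0, 82.9 against 88.3); the simulated range runs from negligible to several points. All of this rests on assumed curves, and the third example and the simulation also assume that permitted release is taken at once. Release is not compulsory, and Tables 2 and 3 schedule collection to Day 7 (168 h). If every volunteer stays that long, the problem is confined to later collections.

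Because the affected summaries serve the primary objective and the correction is simple, the wording should be corrected before analysis.

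**What to change.** Change the analysis text only; the rules on residence and collection need no change for this purpose.

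1. In Section 12.2.1, exempt excreta collections after protocol-permitted release from the missing-completely-at-random, no-action rule, and describe them as planned truncation that depends on measured recovery.
2. In the cumulative tables and figures of Section 12.2.2, carry each released volunteer's cumulative recovery at release forward, labelled as a lower bound, so that all released men contribute at every later time and release cannot make the mean fall.
3. Show the number still collecting at every interval. State that interval means after the first release describe only those men and are not to be summed.
4. Base headline recovery in urine, in faeces and in total on per-volunteer values at end of collection.
5. Flag volunteers who withdrew before meeting a release criterion, and show overall recovery with and without them.

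The cost is a few sentences and an added row of counts. The one downside is that carried-forward values slightly understate any excretion after release. In the third example the carried-forward mean at Day 7 is 90.3%, against 92.5% on the assumed curves had collection continued, a gap of 2.2 points. The lower-bound label tells the reader so.

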12.2.2 Pharmacokinetics

A listing of PK blood sample collection times as well as derived sampling time deviations will be provided. A listing of individual urine sample collection start and stop dates/times as well as urine volumes will be provided for each urine collection. A listing of individual faecal sample collection start and stop dates/times as well as sample weights will be provided. Faecal weight will be reported by both the study centre (collected) and the bioanalytical laboratory (re-weighed for processing).

Pharmacokinetic variables will be summarised using appropriate descriptive statistics (eg, n, arithmetic mean, CV%, SD, geometric mean, geometric coefficient of variation [GCV%], min, median, and max). The geometric mean is calculated as the exponential of the arithmetic mean calculated from individual observations on a log scale. The GCV% is calculated as $100 \cdot \sqrt{(\exp(s^2) - 1)}$ where s is the SD of the data on a log scale. Mean, SD, CV%, geometric mean, and GCV% will not be calculated for t_{max} .

Plasma concentrations that are below the lower limit of quantification (LLOQ) will be handled as follows:

- At a time point where less than or equal to 50% of the values are below the LLOQ (BLQ), all BLQ values will be set to LLOQ, and all descriptive statistics will be calculated.
- At a time point where more than half of the values are BLQ, the mean, SD, geometric mean, and CV% will be set to Not Determined (ND). The max value will be reported from the individual data, and the min and median will be set to BLQ.
- If all values are BLQ at a time point, no descriptive statistics will be calculated for that time point. Not applicable (NA) will be written in the field for SD and CV% and BLQ will be written in fields for mean, geometric mean, min, median, and max.
- The number of BLQ values (n below LLOQ) will be reported for each time point.

A subject listing of all concentration-time data will be presented along with the descriptive statistics for all healthy volunteers. Figures of geometric mean concentration-time data will

be presented for plasma and whole blood [^{14}C] radioactivity concentrations and plasma selumetinib and N-desmethyl selumetinib concentrations combined, as appropriate. Individual subject concentration-time data for the respective blood-based analyte combination will be graphically presented on linear and semi-logarithmic scales.

The ratio of plasma selumetinib to plasma [^{14}C] radioactivity concentrations (expressed as a percentage) as well as the ratio of plasma N-desmethyl selumetinib to plasma [^{14}C] radioactivity concentrations (expressed as a percentage) for each sampling time will be listed by healthy volunteer and summarised using descriptive statistics, to assess the contribution of unchanged drug to the total radioactivity in plasma over time.

A subject listing of whole blood/plasma [^{14}C] radioactivity concentration-time ratios (expressed as a percentage) and percent distribution of radioactivity in blood cells will be presented and the data will be summarised by scheduled time using descriptive statistics.

Blood-based PK parameters will be summarised using descriptive statistics. Individual PK parameters will be presented along with descriptive statistics for all healthy volunteers.

Urine [^{14}C] radioactivity data will be summarised by scheduled collection intervals using descriptive statistics. Individual urine recovery data will be presented along with the descriptive statistics for all healthy volunteers.

Faecal [^{14}C] radioactivity data will be summarised using descriptive statistics. Individual faecal recovery data will be presented along with the descriptive statistics for all healthy volunteers.

The total recovery of radioactivity over the study duration will be computed as the sum of the cumulative excretion (as % of dose) in urine, faeces, and emesis (if any). Cumulative mean recovery of radioactivity-time profiles will be graphically presented for urine, faeces, and total (sum of urine plus faeces, plus emesis, if applicable). Individual cumulative recovery data (urine, faeces, and total) will be presented graphically and in tables along with the descriptive statistics for all healthy volunteers.

12.2.2.1 Interim analysis

The bioanalytical laboratory will calculate percent of radioactive dose recovered in urine and faeces in support of healthy volunteer release criteria. These values will be used for interim reporting purposes only to track radioactive dose recovered on an ongoing basis. These results will be part of the radioactivity report which will be included as an appendix to the CSR. Following database lock, the percent of radioactive dose recovered in urine, faeces, and overall, and related parameters will be calculated following Standard Operating Procedures (SOPs) and rounding procedures as described above and in Section 11.4. The values calculated by will be considered the final study results and presented in the body of the CSR.

12.2.3 Safety and tolerability measurements

All safety data (scheduled and unscheduled) will be presented in the data listings. Continuous variables will be summarised using descriptive statistics (n, mean, SD, min, median, max). Categorical variables will be summarised in frequency tables (frequency and proportion). Graphical presentations may be used as appropriate. Examples may include line graphs showing individual or mean development over time, and shift plots showing pre-treatment values on horizontal axis and post-treatment values on vertical axis.

All AEs will be collected for each healthy volunteer from the time of informed consent until Day 7 or the last day of urine/faecal collection (whichever is later). Adverse events that occur before administration will be reported separately.

Adverse events will be summarised by Preferred Term and System Organ Class using MedDRA vocabulary. Furthermore, listings of SAEs and AEs that led to withdrawal will be made and the number of healthy volunteers who had any AEs, SAEs, AEs that led to withdrawal, and AEs with severe intensity will be summarised.

Tabulations and listings of data for vital signs (blood pressure, pulse rate, and body temperature), and clinical laboratory tests will be presented. Where applicable, data will be summarised for the absolute value at each scheduled assessment, and for the corresponding change from baseline. For clinical laboratory tests, listings of values for each healthy volunteer will be presented with abnormal or out-of-range values flagged. Clinical laboratory data will be reported in Système International (SI) units (where available) in the CSR.

Results from the physical examinations, ECGs, echocardiograms, and eye examinations will be presented in listings only.

Extra measurements (such as unscheduled or repeat assessments) will not be included in the descriptive statistics, but will be included in subject listings.

